#### **4.1.1 Patient Contact and Screening**

Pre-screening of patients' charts by our recruitment team prior to patient contact helps to ensure that only potentially eligible candidates who meet initial criteria (e.g., age, breast cancer diagnosis and stage, ECOG score, English speaking status) will be contacted regarding participation in the study in order to minimize potential patient burden.

Patients recruited through community-based methods or the CSC will be identified as described above and screening will proceed as described next. For the women recruited through the email blasts to Cancer Experience Registry members, several emails may be sent to facilitate recruitment efforts. All women recruited through the CSC will be given information about the study (e.g., study letter, brochure or informational handout) and study contact information.

The initial contact for FCCC and Temple patients will be conducted with approval from the treating physician/provider and will be from the research team and/or the treating provider. For patients identified through the FCCC and TUH registries, lists of potentially eligible candidates will be approved by the patients' provider (e.g., their treating provider at FCCC or [name] at TUH) prior to sending the introductory letter and the brochure and/or flyer. TUH patients will receive the same recruitment materials as FCCC patients. Potential candidates who have not called to opt out of the study or otherwise opted out will be called by a research member to confirm their eligibility.

For interested candidates, screening will determine eligibility and will also include a discussion of study procedures, risks, benefits, and the voluntary nature of their participation, and the fact that it will not affect their medical care if they are a patient at FCCC. Screening the patient for eligibility may occur over the telephone or in person and will include assessment of age, disease status and stage, partner status and age, treatment status and length of time since completing treatment, use of hormone therapy, hearing impairment of patient and partner, current pregnancy, past history of breast or gynecological cancer, current treatment for a concurrent cancer, current participation in marital therapy, and sexual concerns. We used many similar items, including the sexual concerns screening item, in the pilot protocol 15-8007 and have had success with these screening items. Medical record review for all patients will confirm the patients' breast cancer diagnosis, stage, and treatment status, as described in the screening script (or in pre-screening). We will use separate screening scripts for women recruited through site-based versus community-based methods because for women recruited through community-based methods, we will need permission from their clinicians to review their medical records.

Patient eligibility screening will occur privately due to the sensitive nature of the questions and using methods we employed successfully in our R21-funded pilot randomized controlled trial. In order to collect valuable eligibility data about the target population that could be used to inform our development of future studies, all screening items will be administered, and the data will be recorded if patients endorse the item allowing us to keep the information obtained during the screening discussion.

If the patient is eligible and is considering participation in the study, the study team member will obtain permission from the patient to contact the patient's spouse or partner with regard to participation, as described in the Screening Script. Partners will be screened for the purpose of determining their interest in participating in this study; there are few specific eligibility criteria for the partner (see criteria in Table 1 below), which will be determined during the patient's screening. To ensure adequate understanding of the study by both members of the couple prior to consenting, a study team member will speak personally with both members of the couple in order to ascertain an adequate level of understanding by both members of the couple prior to giving them permission to consent for the study and proceed with enrolling.

The patient may prefer to speak with the spouse/partner initially herself. In this case, the recruiter may follow-up with the patient at a later time to assess continued interest and to speak with the spouse/partner to describe the study and/or gauge understanding of the study procedures. The recruiter may also email the partner with a separate recruitment email and study flyer designed to describe the study to partners. The partner flyer may also be given to the patient to share with her partner, if the patient is unwilling to provide her partner's contact information at that time. In the case of in-person recruitment, the recruiter will nevertheless ask for permission to discuss the study with the partner, although the patient screening will occur in private (unless the patient indicates a preference for having the partner present during the discussion).

Patients recruited from the community will be asked to provide a medical record release so that their medical eligibility may be confirmed with their breast cancer providers prior to enrollment. Only patients who screen in as likely eligible during the initial recruitment screening call will be asked to provide authorization for release of their medical records (See 9.1 Consent Process for Intervention Study for more information about the medical records release form). Patients who do not authorize release of their medical records in order to confirm eligibility will not be enrolled on study.

Patients who decline to participate in the intervention study will be approached to complete a developmental survey (Exploratory Aim 2) assessing their reasons for nonparticipation and potential preferences for similar interventions.

#### **4.1.2 Participant Reimbursement**

Patients and partners in the study will receive compensation in differing amounts after completion of individual surveys using amounts consistent to those used in prior couple-based intervention studies conducted by the study team: pre-treatment/baseline (\$25 per person, \$50 per couple); post-treatment (\$25 per person, \$50 per couple); 3-month follow-up (\$40 per person/\$80 per couple), and 6-month follow-up (\$50 per person, \$100 per couple). The total possible compensation is \$140 per person (\$280 per couple). Compensation will be provided in the form of gift cards.

Study-eligible patients who refuse the intervention study but complete brief exploratory surveys ("intervention refusers") will receive \$10 for participation, also in the form of gift cards. Regardless of the method of reimbursement, a research team member will confirm receipt of the compensation and will document this in our research files.

Gift cards will be sent individually via US Mail upon receipt of the participant's survey, but may also be given in person if the patient is seen in clinic. Participants will be asked to sign a document confirming receipt of their gift card and will mail back to the study team. Once payment confirmation has been received, the study team member will document this in our research files.

#### **4.1.3 Inclusion and Exclusion Criteria**

Overall, eligible patients for this study will be adult ( $\geq 18$  years) partnered breast cancer patients who have completed active treatment for stage T1-T4, N0-N2, M0 non-recurrent breast cancer between 6 months and 5 years prior who report sexual concerns (see Table 1). Patients' spouses or partners must also be  $\geq 18$  years old.

Table 1. Inclusion Criteria	

• Female

• Age <math>\geq 18</math> years

• Has a medically confirmed diagnosis of non-recurrent breast cancer (Stages T1-T4, N0-N2, M0)

• Completed active treatment (e.g., chemotherapy, radiation therapy, surgery, immunotherapy) 6 months-5 years ago (current use of endocrine therapy is acceptable)

• Is currently in a partnered relationship that could involve sexual activity (as determined by eligibility screening script)

• Has a partner or spouse who is <math>\geq 18</math>

• Lives with a romantic partner <math>\geq 6</math> months

• Score of <math>\geq 3</math> on Patient Care Monitor Sexual Concerns screening item^47

	
Exclusion Criteria	

• Patient or partner is not able to speak and read English, as stated in medical record, as observed by study team member or in self-report

• Patient or partner ECOG Performance score <math>> 2</math> OR medically unable to participate as judged by physician/in medical record or by self-report

• Patient or partner has a hearing impairment

• Patient and partner do not have reliable telephone access

• Patient has overt cognitive dysfunction or psychiatric disturbance such as suicidal ideation or severe mental illness, as observed or judged by the researcher, physician or referring source, or self-report

• Patient past or current history of any cancer other than non-melanoma skin cancer, including prior breast cancer

• Patient is currently participating in couple/marital therapy

• Patient is currently pregnant

	

Because male breast cancer patients may experience unique sexuality concerns, we will recruit only female breast cancer patients for the study patient sample. There are no exclusions based on race or ethnicity and every effort will be made to include a diverse patient sample for the current study.

Patients are excluded if they are currently participating in couple or marital therapy to avoid confounding improvement in the IE intervention with improvement in co-occurring therapy. Further, we also exclude patients with past or current history of breast or other cancers, as such patients may have prior sexual complaints and have different needs. Pregnant patients are also excluded because they may have different sexual function and sexual concerns. Patients and partners with a hearing impairment are excluded due to the nature of this intervention as occurring over the telephone and therefore requiring active listening. Non-English speakers are similarly excluded. Patients who are medically unable to participate, as determined through an ECOG score, self-report, medical record, or provider, are excluded because participants are asked to engage in behavioral exercises between intervention sessions and such patients may not be able to participate fully in these study activities; similarly, if patients deem their partners medically unable the couple will be ineligible. Finally, because we are collecting outcome data on patients' psychological distress and well-being, and because cognitive dysfunction and psychiatric illness could interfere with study activities, patients with overt cognitive dysfunction and psychiatric disturbance are excluded, as described above in Table 1. No exclusions will be made for any

part of the investigation based on sexual orientation, which means that same-sex couples may participate.

Participants in Aim 2 completing the developmental surveys are patients who meet eligibility criteria for the pilot trial (Aim 2) but decline to participate in the trial. This may be because they do not have time or interest in participating in the full trial or for other reasons, and the developmental survey study allows them the opportunity to contribute to these research efforts in a different way.

## **4.2 Data Collection and Measures**

### **4.2.1 Medical Data Collection**

Because patient self-report about medical history can occasionally differ from the data on the same items in patients' charts (e.g., treatments received), we will collect the following data on enrolled patients through medical chart review: date of diagnosis and disease stage, dates and types of treatments and surgeries received for breast cancer, current treatment status, current medication use (including endocrine therapies), and current menopausal status. The data abstraction will be performed by study staff and entered into our de-identified databases. This medical chart review is documented in the consent form. We will also ask study candidates permission to keep the medical data (and other data) we collect during the screening process so that we may compare candidates who end up agreeing to participate in the study versus do not agree on these variables.

### **4.2.2 Self-Report Data Collection**

An overview of study measures and collection time points for participants, including number of items in each scale, is in **Table 2**. After consenting, patients and partners will complete outcome measures at baseline, post-intervention, 3-month follow-up, and 6-month follow-up through a web portal on their home computers using REDCap.

REDCap is a secure, web-based application that is flexible enough to be used for a wide variety of research studies, offers intuitive interfaces for data entry and real time data validation, and supports easy data manipulation with audit trails and reporting capabilities, including automated export to common statistical packages. REDCap for electronic data collection is preferred over paper and pencil administration for this study because: (1) it can be completed in less time and is therefore potentially less burdensome for participants; (2) it is less burdensome to the investigators in terms of both collection and data entry – essentially eliminating the need for by-hand data entry of self-report measures; (3) it leads to fewer human errors because it obviates the need for by-hand data entry. Participants without computer or internet access will be able to complete data collection through US Mail using paper and pencil versions of the electronic data forms, sent to the couple by a study team member. If sent through US Mail, surveys will be sent (along with consent forms, if necessary) in separate envelopes with instructions to complete these independently from one another.

### **4.2.3 Self Report Measures**

#### **4.2.3.1 Primary Outcome Measure (Primary Aim)**

Patient Sexual Function. Patients will complete the primary outcome measure, i.e., the 19-item Female Sexual Function Index (FSFI), at all four time points (T1-T4). The FSFI is a widely used sexual function measure with established validity in breast cancer. The FSFI is an optimal primary outcome measure because it is comprehensive and multi-dimensional, in that it assesses biological, psychological, and social dimensions of women's sexual experiences including desire, arousal, pain, and satisfaction with sexual relationship, all of which may change due to participation in the IE intervention. Further, in our breast cancer pilot trial, we found a very large effect size for patient sexual function (Cohen's  $d=1.30$ ). The total score will be used as the primary endpoint as it reflects women's overall sexual

function. In addition, we will conduct separate models for each sexual function domain as a supplemental analysis to clarify which domains of sexual function may be driving any effects on overall function. FSFI scores are sensitive to increases in response to participation in behavioral (non-medical) intervention trials in women with cancer up to the proposed 6-month time point.

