### **13.2 Statistical Analyses for Aim 1 (Primary Aim; Effects of IE Intervention on Patient Sexual Function)**

The primary analysis will examine whether, relative to the LHT condition, the IE condition leads to greater increases in the primary outcome of patient sexual function at all three post-treatment assessments (T2-4; post-treatment; 3-month FU; 6-month FU). We will also examine specific domains of sexual function (satisfaction, desire, arousal, lubrication, orgasm, pain) separately. In a mixed effects regression model, study condition will serve as the independent variable and patient sexual function at each time point will serve as the dependent variable; pre-treatment sexual function will be included in the model as a covariate with time included as a categorical covariate. Intervention by time interaction effects will be included to test the intervention effect at each follow-up time. Subject-specific random intercepts will account for within-subject variability. Intervention effects on patient sexual function at each follow-up are tested using F tests of combined main and interaction effects.

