### **13.8 Power Calculations**

Power calculations are based on Aim 1 (Primary Aim). On the patient sexual function measure, a change of 5 points would be considered clinically meaningful (scale range: 2-36,  $SD \approx 10$ ). Based on pilot data, we anticipate that the  $SD$  of the change scores will be 8.2. Using our prior IE trials to guide attrition estimates, we estimate an attrition rate of 24% at 6-month follow-up, resulting in data available from 92 analyzable couples at 6-month follow-up. We will therefore have 82% power to detect a difference of 5 points in change scores, assuming a 2-sided test with type-I error ( $\alpha$ ) of 0.05. In our breast cancer pilot study, we found a between-groups difference in change scores on patient sexual function of 10.7 at post-treatment. Based on results of similar trials, we expect some attenuation of effects by 6-month follow-up. This study is powered to detect a clinically meaningful change  $> (.5 * \text{main effect})$  through the final assessment point. In sum, the study is conservatively powered to detect an effect of the IE intervention approximately half the size obtained in the pilot trial. The sample size of 120 couples (240 participants) was selected based on these calculations.

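### The separate FSFI domain models are meant to show which domains drive the total-score effect, but no planned analysis compares one domain with another

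*Combined protocol and SAP*

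**What the plan says.** Section 4.2.3.1 makes the FSFI total score the primary endpoint. It then adds "separate models for each sexual function domain as a supplemental analysis to clarify which domains of sexual function may be driving any effects" seen on overall function.

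Section 13.2 names the six domains: "We will also examine specific domains of sexual function (satisfaction, desire, arousal, lubrication, orgasm, pain) separately". The model it describes is a mixed effects regression of follow-up sexual function on study condition, with baseline sexual function and categorical time as covariates. On testing it says "Intervention by time interaction effects will be included to test the intervention effect at each follow-up time", and that these effects are "tested using F tests of combined main and interaction effects". The natural reading is that each domain gets the same model as the total.

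Neither section, nor any other, gives a joint model across domains, an intervention-by-domain term, an interval for the difference between two domain effects, or a rule for calling a domain a driver of the total.

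**The concern.** The stated question is relative: do some domains carry more of the effect than others? The tests described answer a different question, six times at each of three follow-ups (6 × 3 = 18 tests): is this domain's effect zero? A domain with p<0.05 beside one with p>0.05 does not show that the two effects differ, because the difference itself has not been estimated or tested.

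At stake is a secondary scientific statement, for example that the intervention acts on desire but not on pain. If the intervention in fact moved all domains alike, sampling error alone could produce a pattern that invites that statement, and nothing in the plan would check it.

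**Working it through.** **Inputs from section 13.8.** A 5-point difference in FSFI change; the SD "of the change scores will be 8.2"; 92 analysable couples at 6 months; two-sided 0.05. With 1:1 allocation (section 4.3) that is 46 per arm. The pilot difference was 10.7 points at post-treatment. From section 13.2: six domains.

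**The plan's own figure.** The noncentrality is 5 / (8.2 × √(2/46)) = 2.92. Power is 82.5% by the noncentral t with 90 df and 83.3% by the normal approximation. The stated 82% is reproduced.

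**Assumptions the documents do not supply.** The total is the sum of six domain scores with equal variances and a common correlation ρ between domain changes; every domain has the same true effect, 5/6 = 0.83 points; one follow-up; unadjusted change scores. No inter-domain correlation or domain SD is given, so ρ is varied.

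**Formulae.** Domain SD: σ = 8.2 / √(6 + 30ρ). Standardised domain effect: d = 0.83/σ. Approximate power per domain: Φ(d × √(46/2) − 1.96). At ρ = 0.5, σ = 8.2/√21 = 1.79, d = 0.47 and power is 61%, against 82% for the total.

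**Simulation, 20,000 trials per setting.** Each domain is tested at two-sided 0.05 by a two-sample t test. The joint test is a 5-df Hotelling test that the six effects are equal.

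| ρ | σ | d | Power per domain | 1–5 of 6 significant, all trials | 1–5 of 6, given a significant total | 1–3 of 6, given a significant total | Joint test rejects |
|---|---|---|---|---|---|---|---|
| 0.3 | 2.12 | 0.39 | 47% | 84% | 91% | 55% | 4.9% |
| 0.5 | 1.79 | 0.47 | 61% | 70% | 73% | 32% | 5.0% |
| 0.7 | 1.58 | 0.53 | 72% | 49% | 47% | 16% | 5.2% |
| 0.8 | 1.50 | 0.56 | 76% | 37% | 34% | 10% | 5.2% |

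Repeat runs differ by about one percentage point.

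**Baseline adjustment.** Section 13.2 adjusts for baseline; the table does not. Section 13.8 gives an SD of about 10 for the score. If the variance is the same before and after, 8.2² = 2 × 10² × (1 − r), so r = 0.66. The adjusted SD is 10 × √(1 − 0.66²) ≈ 7.5 and the total's d is 5/7.5 = 0.67. The 1–5 of 6 pattern then occurs in about 83%, 65%, 42% and 30% of all trials at ρ = 0.3, 0.5, 0.7 and 0.8.

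**Pilot effect.** At 10.7 points all six domains are significant in roughly 90% of trials at ρ = 0.3 and roughly 99% or more from 0.5 up, so a mixed pattern is rare. Section 13.8 itself expects some attenuation by 6 months and sizes the trial at about half the pilot effect.

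**The case against.** The strongest reply is that the reading rule behind these percentages is not in the plan. Neither section says that a domain drives the effect when p<0.05 and does not otherwise. A reader might infer such a rule, since F tests are the only criterion section 13.2 describes, but the documents do not state it. This stands: the percentages show what that rule would do, not what the plan commits to.

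Second, separate models can inform the question through estimation. If the total is the sum of the domain scores, differences in domain change add up to the difference in total change, so each estimate in points describes that domain's contribution. This also stands, and the fix keeps it. But contributions still need an interval for the difference between them before one is called larger, and none is planned.

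Third, equality of standardised effects is only one possible null. If domain SDs differ, equal standardised effects are not equal contributions in points. This argues for reporting both scales and against forbidding every domain statement unless one test of modest power is significant.

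Fourth, the analysis is labelled supplemental and worded cautiously. It does not touch the primary test. A reader might also fear that it would misdirect later tailoring of the intervention, but the only tailoring rule in the plan (section 13.6) concerns age and race/ethnicity.

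**Conclusion.** The point holds in a limited form. The domain models are given a comparative purpose, and no planned test or interval compares domains. The primary conclusion on the FSFI total is unaffected.

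The size is conditional. If domains were sorted by p<0.05, equal true effects at the design values would give a mixed pattern at one follow-up in about 84% to 37% of trials for ρ from 0.3 to 0.8. The figure is somewhat lower with baseline adjustment and small at the pilot effect. A joint test would wrongly declare a difference in about 5%. These figures rest on equal domain variances, a common correlation that the documents do not give, and a total that is the sum of the domains. Other values would move the percentages but would not supply the missing comparison.

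A stronger reading is tempting: that equal effects would usually look like a few driving domains. The figures do not support it. Given a significant total, 1 to 3 significant domains is the majority result at ρ = 0.3 (55%) but not at 0.5 (32%) or above. At ρ of 0.7 or more the most common single result is that all six are significant.

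**What to change.** Keep the six domain models as supplemental. In sections 4.2.3.1 and 13.2, add the following:

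- Report each domain's intervention effect at each follow-up with a 95% CI, in FSFI points (its contribution to the total) and on a standardised scale.
- Add one supplemental joint model of the six domain scores, with domain as a within-patient factor and an unstructured covariance across domains. Include an intervention-by-domain test and CIs for differences between domain effects. State in advance which scale the test uses.
- Base any statement that some domains drive the effect more than others on that comparison, not on which domains reach p<0.05. Otherwise describe the domain estimates without ranking them.

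The cost is one extra supplemental model and a few sentences in the plan; no new data are needed. The drawback is that the between-domain comparison has modest power, so the trial may make fewer domain-specific statements.
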